Appendix 1.2 Events for the Open-label Safety Extension Period and Safety Follow-up Period

Events	OL Safety Extension Period (24 weeks)					Safety Follow-up Period (2 weeks)	
	OL Treatment						
Weeks (W) ^a	OLE W2	OLE W6	OLE W10	OLE W14	OLE W18	OLE W22	End OLE / ET Visit ^c
Window (Days)	7-21	35-49	63-77	91-105	119-133	147-161	161-175
Window Relative to	End DBRW	End DBRW	End DBRW	End DBRW	End DBRW	End DBRW	End DBRW
Physical Exam ^d							
Weight	X	X	X	X	X ^a	X ^a	X
Vital Signs ^e	X	X	X	X	X ^a	X ^a	X
Hematology, Chemistry							
Urinalysis							X
Urine drug screen	X	X	X	X	X ^a	X ^a	X
Breath alcohol test	X	X	X	X	X ^a	X ^a	X
Urine/Serum pregnancy test ^f	X	X	X ^b	X	X ^{ab}	X ^{ab}	X ^f
12-lead ECG							X
ESS	X	X	X	X			X
CGlc	X	X	X	X			X
PGlc	X	X	X	X			X
IHSS	X	X	X	X			X
FOSQ-10							X
WPAI:SHP							X
C-SSRS Since Last Visit Version	X	X	X	X	X	X	X

Appendix 1.2 Events for the Open-label Safety Extension Period and Safety Follow-up Period

Events	OL Safety Extension Period (24 weeks)					Safety Follow-up Period (2 weeks)	
	OL Treatment						
Weeks (W) ^a	OLE W2	OLE W6	OLE W10 In Clinic or Call ^b	OLE W14	OLE W18 In Clinic or Call ^b	OLE W22 In Clinic or Call ^b	End OLE / ET Visit ^c
Window (Days)	7-21	35-49	63-77	91-105	119-133	147-161	161-175
Window Relative to	End DBRW	End DBRW	End DBRW	End DBRW	End DBRW	End DBRW	End DBRW
Assess subject and determine if additional dose titration is necessary	X	X					
Assess tolerability to current dose			X	X	X	X	
Dispense Study Drug ^g	X	X	X ^b	X	X ^b	X ^b	
Collect Study Drug, Measure compliance	X	X		X			X
AE Reporting	X	X	X	X	X	X	X
Concomitant Medications	X	X	X	X	X	X	X
PK Study ^h					X		

AE = adverse event; CGIC = Clinical Global Impression of change; C-SSRS = Columbia-Suicide Severity Rating Scale; DBRW = double-blind randomized withdrawal; ECG = electrocardiogram; ESS = Epworth Sleepiness Scale; FOSQ-10 = Functional Outcomes of Sleep Questionnaire, short form; IHSS = Idiopathic Hypersomnia Severity Scale; OL = open-label; OLE = open-label extension; PGIC = Patient Global Impression of change; PHAQ = pharmacokinetics; WOCBP = Women of Child Bearing Potential; W = week; WPAI-SHP = Work Productivity and Activity Impairment Questionnaire: Specific Health Problem

^a Visits conducted by phone call are shaded in grey. If a phone visit is conducted in clinic, assessments noted should be performed.

^b Phone visit may be converted to a clinic visit if required due to local regulations. If these visits are in-clinic visits, dispensing of JZP-258 may occur and urine pregnancy testing should be completed for WOCBP.

^c For all subjects who prematurely discontinue during the Double-blind Randomized Withdrawal Period, an attempt should be made to perform all procedures associated with the End of Double-blind Randomized Withdrawal Visit. For all subjects who prematurely discontinue during periods other than the Double-blind Randomized Withdrawal Period, an attempt should be made to perform all procedures associated with the End of Open-label Extension Visit.

^d The Physical Exam includes a brief neurological exam, excludes genitourinary.

^e Vital signs include blood pressure, pulse/heart rate, body temperature, and respiratory rate. BP should be measured after the subject has been resting at least 5 minutes. On PK Nights, vital signs will be measured at the times specified in the schedule of events for the PK substudy (see [Appendix 1.3](#) and [Appendix 1.4](#)).

^f Serum pregnancy tests (end of open-label extension/early termination visit only) and urine pregnancy tests will be performed in WOCBP if the visit is performed in clinic.

^g Subjects will start the Open-label Safety Extension Period at a dose no higher than the dose they received at the end of the Stable Dose Period. A lower starting dose will be allowed at the discretion of the Investigator. If further titration is required, it will proceed at a rate of ≤ 1.5 g per week during this period, not to exceed a maximum total dose of 9 g/night.

^h A PK substudy for subjects during either the Open-label Treatment Titration and Optimization Period or Open-label Safety Extension Period (Appendix 1.3 and Section 7.7).

Appendix 1.3 Schedule of Events for PK Night (1 Night During Open-Label Treatment and Titration Optimization Period or Open-Label Safety Extension Period) Once Nightly JZP-258 Dosing Regimen

Procedure	PK Night timepoints (hours); All timepoints postdose unless specified							Notes
	Prior to PK dosing	Pre Dose	0.5h ± 5 min	0.75h ± 5 min	1h ± 5 min	1.5h ± 15 min	2h ± 15 min	4h ± 15 min
Informed consent	X							
Record meal time/content in the eCRF ^a	X							
Vital Signs ^b Includes supine blood pressure, pulse/heart rate, and respiratory rate	X (include body temp)	X	X	X	X	X	X (include body temp)	X
Concomitant Medications	X							
Pulse Oximetry ^c								
Urine drug screen	X							
Breath alcohol test	X							
Urine pregnancy test (WOCBP) ^d	X							
Efficacy Assessments (predose) ^e : ESS, , CGIC, PGIC, IHSS, FOSQ-10, WPAI-SHP, C-SSRS Since Last Visit Version	X ^e							Assessments only to be performed if the visit is unscheduled. All assessments to be completed prior to first dose of JZP-258.

Appendix 1.3 Schedule of Events for PK Night (1 Night During Open-Label Treatment and Titration Optimization Period or Open-Label Safety Extension Period) Once Nightly JZP-258 Dosing Regimen

Procedure	PK Night timepoints (hours); All timepoints postdose unless specified							Notes
	Prior to PK dosing	Pre Dose	0.5h ± 5 min	0.75h ± 5 min	1 h ± 5 min	1.5 h ± 15 min	2h ± 15 min	4h ± 15 min
Administer/supervise JZP-258 dose from subject's study drug supply or Dispense Study Drug (if applicable) ^f	X							
Record time of dose(s) ^g	X							
Blood samples for once nightly dosing ^h	X	X	X	X	X	X	X	
Record any AEs								
Brief neurological exam ⁱ							X	

-----Continuous monitoring-----

Assessment should occur the morning after PK assessment to assess for sleepiness.

Appendix 1.3 Schedule of Events for PK Night (1 Night During Open-Label Treatment and Titration Optimization Period or Open-Label Safety Extension Period) Once Nightly JZP-258 Dosing Regimen

Procedure	PK Night timepoints (hours); All timepoints postdose unless specified								Notes
	Prior to PK dosing	Pre Dose	0.5h ± 5 min	0.75h ± 5 min	1h ± 5 min	1.5h ± 15 min	2h ± 15 min	4h ± 15 min	
BP= blood pressure; C-Glc= Clinical global impression of change; C-SSRS= Columbia suicide severity rating scale; eCRF = electronic case report form; ESS= Epworth Sleepiness Scale; FOSQ-10= Functional Outcome of Sleep Questionnaire short version; h= hours; IHSS = Idiopathic Hypersomnia Severity Scale; IxRS= interactive web/voice response technology; PGlc= patient global impression of change; PK = pharmacokinetics; WOCBP= women of childbearing potential; WPAI-SHP= work productivity and activity impairment questionnaire: specific health problem									
^a Subjects are instructed to take their usual meal at their normal time. The meal may be taken at the clinic or at home, without regard to dosing.									
^b Vital signs include supine blood pressure, pulse/heart rate, body temperature (prior to dosing and 8 hours postdose only), and respiratory rate. Obtain vital signs after subject has been resting for ≥5 min. If vital signs are measured at the same timepoints as PK blood draws, vital signs should be measured prior to blood draws.									
^c Pulse oximetry is monitored continuously from immediately before first dose through 8 hours after the first dose with recorded measurements as noted. An additional measurement will be taken while the subject is awake and before release from the study center.									
^d Urine pregnancy tests will be performed in women of childbearing potential.									
^e Assessments to be completed prior to the first dose of JZP-258.									
^f Subjects are instructed to bring their nightly dose of JZP-258 to the clinic. In the event they do not bring their dose, dosing is allowed via IxRS.									
^g Administer the subject's nightly dose of JZP-258 as per their usual dosing and regimen, record the time.									
^h Blood samples (2 mL at each time point) will be collected depending on the dose frequency. Blood samples for the once nightly dosing regimen will be collected at 0 (predose), and 0.5, 0.75, 1, 1.5, 2, 4, and 8 hours after dosing. Blood samples must be collected within ± 5 minutes of the protocol-specified time points for those time points ≤1 hour after dosing and within ± 15 minutes of the protocol-specified time points for those longer than 1 hour after dosing (e.g., 4 and 8 hours postdose).									
ⁱ Brief neurological exam before discharge on the morning after PK assessment to assess for sleepiness.									

Appendix 1.4

Schedule of Events for PK Night (1 Night During Open-Label Treatment and Titration Optimization Period or Open-Label Safety Extension Period) Twice Nightly JZP-258 Dosing Regimen

Procedure	Prior to PK dosing	PK Night timepoints (hours) All timepoints post-dose unless specified									
		First Dose					Second Dose				
Pre Dose	0.5h ± 5 min	0.75h ± 5 min	1h ± 5 min	1.5h ± 15 min	PreDose	0.5h ± 5 min	0.75h ± 5 min	1h ± 5 min	1.5h ± 15 min	Notes	
Informed consent	X										
Record meal time/content in the eCRF ^a	X										
Vital Signs ^b Includes supine BP, pulse/heart rate, and respiratory rate	X (include body temp)	X	X	X	X	X	X	X	X ^(include body temp)		
Concomitant Medications	X										
Pulse Oximetry ^c	X	X	X	X	X	X	X	X	X	Continuous monitoring through 8 hours after the first dose with recorded times at predose, 0.5, 1, 1.5 hours after each dose and 8 hours after the first dose.	
										Unscheduled visit only	

Appendix 1.4

Schedule of Events for PK Night (1 Night During Open-Label Treatment and Titration Optimization Period or Open-Label Safety Extension Period) Twice Nightly JZP-258 Dosing Regimen

Procedure	Prior to PK dosing	PK Night timepoints (hours) All timepoints post-dose unless specified										Notes
		First Dose					Second Dose					
Pre Dose	0.5h ± 5 min	0.75h ± 5 min	1h ± 5 min	1.5h ± 15 min	PreDose	0.5h ± 5 min	0.75h ± 5 min	1h ± 5 min	1.5h ± 15 min	Prior to discharge		
Urine drug screen	X											
Breath alcohol test	X											
Urine pregnancy test (WOCBP) ^d	X											
Efficacy Assessments (pre dose) ^e :												
ESS, CGIC, PGIC, IHSS, FOSQ-10, WPA:SHP, C-SSRS Since Last Visit Version	X ^e											
Administer/supervise JZP-258 dose from subject's study drug supply or Dispense Study Drug (if applicable) ^f	X											
Record time of dose(s) ^g	X					X						
Blood samples for twice nightly dosing (per dose) ^h	X	X	X	X	X	X	X	X	X			8 hour sample refers to after the first dose only
Record any AEs												Continuous monitoring-----

Appendix 1.4 Schedule of Events for PK Night (1 Night During Open-Label Treatment and Titration Optimization Period or Open-Label Safety Extension Period) Twice Nightly JZP-258 Dosing Regimen

Procedure	Prior to PK dosing	PK Night timepoints (hours) All timepoints post-dose unless specified										Notes
		First Dose					Second Dose					
Pre Dose	0.5h ± 5 min	0.75h ± 5 min	1h ± 5 min	1.5h ± 15 min	PreDose	0.5h ± 5 min	0.75h ± 5 min	1h ± 5 min	1.5h ± 15 min	Prior to discharge		
Brief neurological exam ⁱ											X	

BP= blood pressure; CGIC= Clinical global impression of change; C-SSRS= Columbia suicide severity rating scale; eCRF= electronic case report form; ESS= Epworth Sleepiness Scale; FOSQ-1.0= Functional Outcome of Sleep Questionnaire short version; h= hours; IHSS = Idiopathic Hypersomnia Severity Scale; IxRS= interactive web/voice response technology; PGIC= patient global impression of change; PK = pharmacokinetics; WOCBP= women of childbearing potential; WPAI:SHP= work productivity and activity impairment questionnaire: specific health problem^a Subjects are instructed to take their usual meal at their normal time. The meal may be taken at the clinic or at home, without regard to dosing.
^b Vital signs include supine blood pressure, pulse/heart rate, body temperature (prior to dosing and 8 hours postdose only), and respiratory rate. Obtain vital signs after subject has been resting for ≥5 min. If vital signs are taken at the same timepoints as PK blood draws, vital signs should be measured prior to blood draws.
^c Pulse oximetry is monitored continuously from immediately before first dose through 8 hours after the first dose with recorded measurements as noted. An additional measurement will be taken while the subject is awake and before release from the study center.
^d Urine pregnancy test will be performed in women of childbearing potential.
^e Assessments to be performed only if the visit is unscheduled. All assessments to be completed prior to first dose of JZP-258.
^f Subjects are instructed to bring their nightly dose of JZP-258 to the clinic. In the event they do not bring their dose, dosing is allowed via IWRs.
^g Administer the subject's nightly dose of JZP-258 as per their usual dosing and regimen and record time.
^h Blood samples (2 mL at each time point) will be collected depending on the dose frequency. Blood samples for the twice nightly dosing regimen will be collected at 0 (predose), and 0.5, 0.75, 1 and 1.5 hours after dosing for each dose administered, with the last sample collected at 8 h after the first dose. Blood samples must be collected within ± 5 minutes of the protocol-specified time points for those time points ≤1 hour after dosing and within ± 15 minutes of the protocol-specified time points for those longer than 1 hour after dosing (e.g., 4 and 8 hours postdose).
ⁱ Brief neurological exam before discharge on the morning after PK assessment to assess for sleepiness

APPENDIX 2. ICSD-2 AND ICSD-3**ICSD-3 Criteria for the Diagnosis of Idiopathic Hypersomnia**

- a. Presence of daily periods of irrepressible need to sleep or daytime lapses into sleep for at least 3 months.
- b. Cataplexy is absent.
- c. A multiple sleep latency test (MSLT) performed according to standard techniques shows fewer than 2 sleep onset in REM periods or no sleep onset REM periods if the REM latency on the preceding polysomnogram was less than or equal to 15 minutes.
- d. The presence of at least 1 of the following:
 - The MSLT show a mean sleep latency of ≤ 8 minutes.
 - Total 24-hour sleep time is ≥ 660 minutes (typically 12-14 hours) on 24-hour polysomnographic monitoring (performed after correction of chronic sleep deprivation), or by wrist actigraphy in association with a sleep log (averaged over at least 7 days with unrestricted sleep).
- e. Insufficient sleep syndrome is ruled out.
- f. The hypersomnolence and/or MSLT findings are not better explained by another sleep disorder, other medical or psychiatric disorder, or use of drugs or medications.

ICSD-2 Criteria for the Diagnosis of Idiopathic Hypersomnia

	IH with Long Sleep	IH without Long Sleep
A.	The patient has a complaint of excessive daytime sleepiness occurring almost daily for at least 3 months.	The patient has a complaint of excessive daytime sleepiness occurring almost daily for at least 3 months.
B.	The patient has prolonged nocturnal sleep time (more than 10 h) documented by interview, actigraphy, or sleep logs. Waking up in the morning or at the end of naps is almost always laborious.	The patient has normal nocturnal sleep (greater than 6 h but less than 10 h), documented by interviews, actigraphy, or sleep logs.
C.	Nocturnal polysomnography has excluded other causes of daytime sleepiness.	Nocturnal polysomnography has excluded other causes of daytime sleepiness.
D.	The polysomnogram demonstrates a short sleep latency and a major sleep period that is prolonged to more than 10 h in duration.	Polysomnography demonstrates a major sleep period that is normal in duration (greater than 6 h but less than 10 h).
E.	If an MSLT is performed following overnight polysomnography, a mean sleep latency of less than 8 min is found and fewer than 2 SOREMPs are recorded. Mean sleep latency in IH with long sleep time has been shown to be 6.2 ± 3.0 min.	An MSLT following overnight polysomnography demonstrates a mean sleep latency of less than 8 min and fewer than 2 SOREMPs. Mean sleep latency in IH has been shown to be 6.2 ± 3.0 min.
F.	The hypersomnia is not better explained by another sleep disorder, medical or neurological disorder, mental disorder, medication use, or substance use disorder.	The hypersomnia is not better explained by another sleep disorder, medical or neurological disorder, mental disorder, medication use, or substance use disorder.

ICSD-3 Criteria for the Diagnosis of Idiopathic Hypersomnia

- A. Presence of daily periods of irrepressible need to sleep or daytime lapses into sleep for at least three months.
- B. Cataplexy is absent
- C. A multiple sleep latency test (MSLT) performed according to standard techniques shows fewer than two sleep onset in REM periods or no sleep onset REM periods if the REM latency on the preceding polysomnogram was less than or equal to 15 minutes.
- D. The presence of at least one of the following:
 - 1. The MSLT show a mean sleep latency of ≤ 8 minutes.
 - 2. Total 24-hour sleep time is ≥ 660 minutes (typically 12-14 hours) on 24-hour polysomnographic monitoring (performed after correction of chronic sleep deprivation), or by wrist actigraphy in association with a sleep log (averaged over at least 7 days with unrestricted sleep).
- E. Insufficient sleep syndrome is ruled out
- F. The hypersomnolence and/or MSLT findings are not better explained by another sleep disorder, other medical or psychiatric disorder, or use of drugs or medications.

ICSD-2 Criteria for the Diagnosis of Idiopathic Hypersomnia

IH with long sleep	IH without long sleep
A. The patient has a complaint of excessive daytime sleepiness occurring almost daily for at least three months.	The patient has a complaint of excessive daytime sleepiness occurring almost daily for at least three months.
B. The patient has prolonged nocturnal sleep time (more than 10 h) documented by interview, actigraphy, or sleep logs. Waking up in the morning or at the end of naps is almost always laborious.	The patient has normal nocturnal sleep (greater than 6 h but less than 10 h), documented by interviews, actigraphy, or sleep logs.
C. Nocturnal polysomnography has excluded other causes of daytime sleepiness.	Nocturnal polysomnography has excluded other causes of daytime sleepiness.
D. The polysomnogram demonstrates a short sleep latency and a major sleep period that is prolonged to more than 10 h in duration.	Polysomnography demonstrates a major sleep period that is normal in duration (greater than 6 h but less than 10 h).
E. If an MSLT is performed following overnight polysomnography, a mean sleep latency of less than 8 min is found and fewer than two SOREMPs are recorded. Mean sleep latency in IH with long sleep time has been shown to be 6.2 ± 3.0 min.	An MSLT following overnight polysomnography demonstrates a mean sleep latency of less than 8 min and fewer than two SOREMPs. Mean sleep latency in IH has been shown to be 6.2 ± 3.0 min.
F. The hypersomnia is not better explained by another sleep disorder, medical or neurological disorder, mental disorder, medication use, or substance use disorder.	The hypersomnia is not better explained by another sleep disorder, medical or neurological disorder, mental disorder, medication use, or substance use disorder.

APPENDIX 3. DOSING DIARY

Study Drug Dosing Diary

To be completed in the morning

Subject Number: _____

Date: _____

How many times did you take your study drug last night?

- 0
- 1
- 2
- 3

APPENDIX 4. SLEEP DIARY AND SLEEP DIARY INSTRUCTIONS

Sleep Diary

ID: _____

SAMPLE			
DATE:	12-Oct-17	Day of the Week	Monday

Questions 1-6 refer to your sleep last night and when you woke up today

1. What time did you get into bed?	9:55 PM		
2. What time did you try to go to sleep?	10:30 PM		
3. How long did it take you to fall asleep?	20 min		
4. How many times did you wake up, not counting your final awakening?	2 times		
5. In total, how long did these awakenings last?	30 min		
6. Was there anything unusual that affected your sleep last night? (Yes/No) If yes, please explain.	I have a cold		

Questions 7 - 9 refer to your wake up today

7. What time was your final awakening?	7:00 AM		
8. What time did you get out of bed for the day?	7:45 AM		

9. Is today an off day (e.g., non-working day/weekend or holiday)? (Yes/No)	No		
Questions 10 – 12 refer to your nap(s) today			
10. How many times did you nap or doze during the day?	2 times		
11. In total, how long did you nap or doze during the day? (add up all naps if you had more than one)	1 hour 10 min		
12. Was there anything unusual about your naps today? (Yes/No) If yes, please explain.	Noise from construction next door interrupted my nap		

General Instructions

What is a Sleep Diary? A sleep diary is designed to gather information about your daily sleep pattern.

How often and when do I fill out the sleep diary? It is necessary for you to complete your sleep diary every day. There will be questions for you to answer first thing in the morning and additional questions to answer at bedtime. The sleep diary should be completed within one hour of getting out of bed in the morning, and again at night before going to bed.

What should I do if I forget to complete the sleep diary? If you forget to complete the sleep diary when you wake up, you will have until midnight (12 AM) to answer the questions. After midnight (12 AM) the sleep diary for the day will no longer be available and you will be prompted to complete the sleep diary for the next day.

What do the words “bed,” “night” and “day” mean on the diary? This diary can be used for people who are awake or asleep at unusual times. In the sleep diary, the word night is the time when you choose to go to bed, and the word “day” is the time when you choose or are required to be awake. The term “bed” means the place where you usually sleep.

Will answering these questions about my sleep keep me awake? This is not usually a problem. You should not worry about giving exact times, and you should not watch the clock. Just give your best estimate.

Sleep Diary Item Instructions

Use the guide below to clarify what is being asked for each item of the Sleep Diary.

1. *What time did you get into bed?* Write the time that you got into bed last night. This may not be the time you began “trying” to fall asleep.

2. *What time did you try to go to sleep?* Record the time that you began “trying” to fall asleep.

3. *How long did it take you to fall asleep?* Beginning at the time you wrote in question 2, how long did it take you to fall asleep.

4. *How many times did you wake up, not counting your final awakening?* Please record how many times you woke up between the time you first fell asleep, including waking up to take study drug at night.

5. *In total, how long did these awakenings last?* What was the total time you were awake between the time you first fell asleep and your final awakening. For example, if you woke 3 times for 20 minutes, 35 minutes, and 15 minutes, add them all up (20 min + 35 min + 15 min = 70 min or 1 hr and 10 min).

6. *Was there anything unusual that affected your sleep last night? (Yes/No) If yes, please explain.* Please mark yes if there were unusual circumstances that affect your sleep (e.g., illness, unusually noisy environment, unusual activities or occasions that impacted your normal sleep.)

7. *What time was your final awakening?* Record the last time you woke up in the morning.

8. *What time did you get out of bed for the day?* What time did you get out of bed with no further attempt at sleeping? This may be different from your final awakening time (e.g., you may have woken up at 6:35 a.m. but did not get out of bed to start your day until 7:20 a.m.)

9. *Is today an off day (e.g., non-working day/weekend or holiday)?* An off day is a day when you are not required or scheduled to do activities. If you are employed, this is usually your day off. However, you may have other scheduled activities in your day (e.g., getting your children to school) that would make the day count as a work day.

10. *How many times did you nap or doze during the day?* A nap is a time you decided to sleep during the day, whether in bed or not in bed. “Dozing” is a time you may have nodded off for a few minutes, without meaning to, such as while watching TV. Count all the times you napped or dozed at any time from when you first got out of bed in the morning until you got into bed again at night.

11. *In total, how long did you nap or doze during the day?* Estimate the total amount of time you spent napping or dozing, in hours and minutes. For instance, if you napped twice, once for 30 minutes and once for 60 minutes, and dozed for 10 minutes, you would answer “1 hour 40 minutes.” If you did not nap or doze, write “N/A” (not applicable).

12. *Was there anything unusual about your naps today? (Yes/No) If yes, please explain.* Please mark yes if there were unusual circumstances that affect your sleep (e.g., illness, unusually noisy environment, unusual activities or occasions that impacted your normal sleep.)

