9. Clinically significant parasomnias (e.g., sleep walking, REM sleep behavior disorder, etc.).
10. History or presence of bipolar and related disorders, schizophrenia, schizophrenia spectrum disorders, or other psychotic disorders according to DSM-5 criteria.
11. Current or past (within 1 year) major depressive episode according to DSM-5 criteria. Subjects with depression under control are allowed per the judgment of the Investigator or the treating physician and the antidepressant treatment has to be stable for at least 6 months prior to Screening and remain stable for the duration of the study.
12. Current suicidal risk as determined from history by presence of active suicidal ideation as indicated by positive response to item No.4 or No.5 on the C-SSRS, or any history of suicide attempt.
13. History or presence of any acutely unstable medical condition, behavioral or psychiatric disorder (including active suicidal ideation) that could affect the safety of the subject or interfere with study efficacy, safety assessments, or the ability of the subject to complete the trial per the judgment of the Investigator.
14. Occupation requiring nighttime shift work or variable shift work with early work start times or other occupations that could affect the safety of the subject per the judgment of the Investigator.
15. Usual bedtime later than 1 AM (0100 hours).
16. Female subjects who are pregnant, nursing, or lactating or plan to become pregnant during the study or within 90 days of study completion.
17. Laboratory value(s) outside the laboratory reference range (e.g., aspartate aminotransferase (AST) or alanine aminotransferase (ALT) >3 x upper limits of normal

Clinical Study Protocol: JZP080-301 Amendment 2

[ULN]) or ECG abnormalities considered to be clinically significant that could affect the safety of the subject or interfere with study efficacy, safety assessments, or the ability of the subject to complete the trial per the judgment of the Investigator. (Note: Screening labs and ECG may be repeated once to assess eligibility.)

18. Excessive caffeine use 1 week prior to Baseline or anticipated excessive use defined as >600 mg/day of caffeine leading up to and throughout the Double-blind Randomized Withdrawal Period.

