7. What time was your final awakening?
8. What time did you get out of bed for the day?

For each subject the mean daily TST will be calculated by week (7 day interval) using the daily values from the last 14 days of each period. The mean score for the interval will be calculated by summing the TST over the 7 days and dividing by the number of days where TST was completed. Specifically, TST is derived by the following formula:

$$\begin{aligned}
 & [\text{day 1 (Q7-Q2)-Q3-Q5+Q11}] + [\text{day 2 (Q7-Q2)-Q3-Q5+Q11}] + [\text{day 3 (Q7-Q2)-Q3-Q5+Q11}] \\
 & + [\text{day 4 (Q7-Q2)-Q3-Q5+Q11}] + [\text{day 5 (Q7-Q2)-Q3-Q5+Q11}] + [\text{day 6 (Q7-Q2)-Q3-Q5+Q11}] \\
 & + [\text{day 7 (Q7-Q2)-Q3-Q5+Q11}] / \text{number of day completed}
 \end{aligned}$$

The change in mean daily 24-hour TST from the last week of the SDP to the last week of the DBWR will be summarized and analyzed similar to the primary efficacy endpoint (refer to section 9.1.1).

The below parameters will also be descriptively summarized by randomized treatment using the daily values from the last 14 days of SDP and DBRW. For each parameter (with the exception of the number of awakenings [Q4] and naps [Q10]) the mean score for the week (7 day interval) will be calculated by summing each item over the 7 days and dividing by the number of days a response was completed, similar to the TST formula above. Q4 and Q10 are collected as ordinal categories; therefore, the modal response over the 7 day interval will be summarized.

- Sleep Latency (mins) = Q3
- Wake after Sleep Onset (WASO) = Q5
- Time in Bed (TIB) = (Q8-Q1)
- Sleep Efficiency (nocturnal TST / TIB) = $((Q7-Q2)-Q3-Q5)/(Q8-Q1)$
- Number of awakenings = Q4
- Number of naps = Q10
- Total nap duration = Q11
- Nocturnal TST = $(Q7-Q2)-Q3-Q5$

9.4.3. Exploratory Endpoint 3

There will be four exploratory endpoints derived from the WPAI:SHP questionnaire. The validity of the WPAI has been established in a number of diseases (Reilly 1993). The WPAI:SHP measures work time missed and work and activity impairment because of IH during the past 7 days. Specifically, the questionnaire includes the following:

1. currently employed
2. how many hours missed from work due to IH
3. how many hours missed from work other reasons
4. how many hours actually worked
5. degree IH affected productivity while working
6. degree IH affected regular activities, other than work at a job

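### The sleep diary closes at midnight, but bedtimes up to 1 AM are eligible and naps are reported at bedtime, so Q11 and that day's 24-hour TST can be lost on late nights

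*Protocol*

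**What the plan says.** Protocol Appendix 4 sets two sittings a day: "There will be questions for you to answer first thing in the morning and additional questions to answer at bedtime". It repeats the timing: "The sleep diary should be completed within one hour of getting out of bed in the morning, and again at night before going to bed". It does not number the bedtime questions, but Q10 to Q12 concern naps on the current day, so a morning sitting cannot answer them. The nap count is defined up to the moment the subject retires for the night: "Count all the times you napped or dozed at any time from when you first got out of bed in the morning until you got" (quote cut short here).

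The closing rule is in the same instructions. A subject who forgets the diary on waking has until midnight. Then "After midnight (12 AM) the sleep diary for the day will no longer be available", and the device prompts for the following day. The instructions also say that the diary suits people with unusual sleep hours, and they define night by when the subject chooses to go to bed.

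Exclusion criterion 15 in Protocol 4.2 removes only usual bedtimes later than 1 AM. Usual bedtimes from midnight to 1 AM inclusive stay eligible.

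SAP 9.4.2 builds 24-hour TST from daily terms of the form "day 1 (Q7-Q2)-Q3-Q5+Q11", where Q11 is total nap duration. The weekly mean is formed by "dividing by the number of days where TST was completed". SAP 7.2.5 averages over non-missing days. It drops a subject from the TST comparison only if every day is missing in the last week of the Stable Dose Period or of the Double-blind Randomized Withdrawal Period.

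**The concern.** Three rules cannot all be followed on a late night: eligibility up to 1 AM, nap questions at bedtime, and closure at midnight. The subject who obeys the bedtime instruction most faithfully is the one who loses the entry. Because Q11 is a term of every daily TST, a blank there removes the day from the 24-hour endpoint even when the night items were completed on time. For a subject who habitually goes to bed after midnight, this could recur through a whole analysis week.

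**Working it through.** The documents state no figure to reproduce. The check is a reading of the rules followed by simple arithmetic.

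**1. Timeline for an eligible subject.** Take a usual bedtime of 00:30.

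- Morning of day D: the night items (last night's sleep and today's awakening) are entered in diary D.
- 00:00 at the end of day D: diary D closes and diary D+1 is prompted.
- 00:30: the bedtime sitting falls due. Q10 to Q12 of diary D have been closed for 30 minutes.

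At the latest eligible usual bedtime of 01:00 the gap is 60 minutes. Criterion 15 concerns the usual bedtime only, so it does not cap any single night. A subject answering at that point could also enter day D's naps under D+1.

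**2. The SAP formula on the protocol's own sample day.** Inputs from the sample column in Appendix 4: Q2 = 22:30, Q7 = 07:00, Q3 = 20 min, Q5 = 30 min, Q11 = 70 min.

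- Q7 − Q2 = 510 min
- Nocturnal sleep = 510 − 20 − 30 = 460 min
- 24-hour TST = 460 + 70 = 530 min

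Without Q11 the second figure is available and the third is not.

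**3. Effect on one analysis week.** Let k be the number of days on which Q11 is locked out. The documents do not give k, so it is assumed and may be 0 to 7. As written, the formula and denominator drop such a day. The SAP has no explicit rule for night items present with Q11 absent, so the last column shows the alternative of counting the blank as 0, using the sample day's 70 min nap on every day: shift = −k × 70 / 7 = −10k min.

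| k | Days left (7 − k) | Share lost (k/7) | Shift in weekly mean if blank counted as 0 |
|---|---|---|---|
| 0 | 7 | 0% | 0 min |
| 1 | 6 | 14% | −10 min |
| 2 | 5 | 29% | −20 min |
| 3 | 4 | 43% | −30 min |
| 7 | 0: subject leaves the TST comparison | 100% | −70 min |

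Appendix 4 asks for N/A when there was no nap. That is a true zero, unlike a locked-out blank, and the SAP does not separate the two.

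**The case against.** The strongest reply is that the loss is avoidable and small.

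- **A subject can answer before midnight.** Someone retiring at 00:30 could complete Q10 to Q12 at 23:45, which is still at night and before bed. The closing time is in the same instructions. This stands: the loss is not certain on every late night. But nothing tells subjects to do so, and the nap window runs until they get into bed, so a later doze would be missed.
- **The midnight limit is introduced for forgotten morning entries.** Its opening sentence is. The sentence that follows closes the whole day's diary, and Q10 to Q12 belong to that day.
- **There is supervision.** Protocol 6.8 has staff review the diary at visits and give reminders at phone contacts. At least two weeks of diary are kept in screening and reviewed at Baseline (Protocol 7.2.1). SAP 9.5.1 describes portal access. These make repeated lockouts easier to notice and total loss of a week less likely, but neither document describes reopening a closed day.
- **The night record survives.** A reader might infer that a lockout makes the whole night's record unusable. The documents do not support that. SAP 9.4.2 separately summarises nocturnal TST, sleep latency, wake after sleep onset, time in bed and sleep efficiency, none of which uses Q11, each averaged over the days with a response. Only 24-hour TST and the nap summaries are exposed.

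**Conclusion.** The point holds as a conflict between the diary rules with a limited consequence. On a night with bedtime after midnight, following the bedtime instruction loses Q10 to Q12 and, on the plain reading of SAP 9.4.2, that day's 24-hour TST. The size runs from nothing (k = 0) to exclusion from the TST comparison (k = 7 in either analysis week). It depends on an undocumented frequency of late nights and on subjects not answering early. The endpoint is exploratory; the primary, key secondary and other secondary endpoints and the nightly TST inclusion criterion do not use Q11.

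A reader might also infer that the lost days are mostly off days and that mean TST is therefore biased low. The documents do not support this, for two reasons.

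- A bedtime after midnight closes the diary of the day just ended, which holds the previous night's sleep and that day's naps. A late Friday night puts Friday's entry at risk (Thursday night's sleep, Friday's naps); the lie-in that follows belongs to Saturday's diary, which is open. A late Saturday night would put an off day's entry at risk. No document says which pattern prevails.
- The endpoint is a change between two weeks, compared between randomized arms under the same closing rule. A common shift would largely cancel unless late nights differ by period and arm.

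The direction of any bias is therefore undetermined. What is established is avoidable missing data.

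**What to change.** Make one of two changes in Appendix 4 and the device set-up:

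- Keep the evening section (Q10 to Q12) open past the latest eligible bedtime, for example to 3 AM, filed under the diary date of the day just ended; or
- Instruct subjects to complete Q10 to Q12 before midnight even if they go to bed later.

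The first costs a device setting and keeps the nap window as defined. The second costs one sentence, but naps taken between the entry and bedtime are missed. Either acts only on diary days still to be collected. No SAP change is needed to preserve nocturnal TST, because SAP 9.4.2 already plans it as a descriptive summary.
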